### 3.8.1 Demographics and Baseline Characteristics

Descriptive statistics will be presented for all patient demographic data and baseline characteristics including age, sex, race, height, employment status, tobacco use, and alcohol use. The summary will include:

- The number and percentage of subjects within each category.
- The sample size, mean, median, SD, minimum, and maximum values for each continuous variable. Age will be calculated as follows: Age = Largest Integer ≤ [(Baseline Visit Date Date of Birth + 1)/365.25]. The midpoint of the year of birth will be considered as the date of birth for each patient.

### 3.8.2 Medical History and Prior PS Treatments

The number and percentage of subjects reporting family history of PS, types of known PS triggers, prior frequency and pattern of flare-ups, concomitant PsA and who have positive

COMPLETE - PS Statistical Analysis Plan Version 3.0 July 23rd, 2015 Page 29 of 231

rheumatoid factor will be summarized. In addition, the number and percentage of patients with other relevant medical history will be summarized by body system.

All previous and current PS medications recorded on the CRF will be coded and summarized according to the generic drug names using the WHO Drug Classifications. Each summary will give the number and percentage of patients who took medications that were coded to each generic drug name, as well as the number and percentage of patients that took any medication at all.

### 3.9 Patient Follow-Up Characteristics

Descriptive statistics comprising the sample size, mean, median, SD and 95% confidence intervals of the mean for continuous variables, and number and percentage of subjects for categorical variables will be used to describe all follow-up patient characteristics including: weight, C-Reactive Protein (CRP), Erythrocyte Sedimentation Rate (ESR), rheumatology consult, clinically important changes in physical examination, patient compliance with treatment, changes in psoriasis medications/treatments, including phototherapy, Psoriasis and Arthritis Screening Questionnaire (PASQ) score, Body Surface Area (BSA), Patient Global Assessment of Disease Activity (VAS), Dermatology Quality of Life Index (DLQI), Beck's Depression Inventory (BDI) score, Medical Outcomes Study Short Form 36 (SF-36) score, Working Limitations Questionnaire (WLQ) score, and Health Care Utilization Questionnaire.

## 3.10 Analysis of the Primary Objective

For the primary objective, between-group differences with respect to achieving a PGA of "0" or "1" at six months will be assessed with simple logistic regression analysis and multivariate logistic regression models adjusting for potential confounders or the propensity score. In addition, a Generalized Estimating Equation (GEE) model will be used to compare

COMPLETE - PS Statistical Analysis Plan Version 3.0 July 23rd, 2015 Page 30 of 231

the three patient groups in terms of achieving a PGA of "0" or "1" over 24 months of treatment. Kaplan Meier based time to event (survival) analysis will be used with the log-rank test to assess the statistical significance of the between group differences. Cox's proportional hazards model will also be used to adjust for potential confounders or the propensity score.

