There are some topical drugs that do not contain corticosteroids, like Dovonex (calcipotriene), and Vertical (calcitriol). Dovonex and Taclonex (calcipotriene and betamethasone dipropionate) have some non-severe side effects, the most common being skin irritation, stinging and burning for Dovonex and itching, rash, skin thinning and burning for Taclonex. Furthermore, the patient has an increased risk of skin tumors because of the sensitivity to light. Some antipsoriatic topical drugs contain retinoids, such as Tazorac (tazarotene). These medications act less rapidly than corticosteroids, but have fewer adverse effects. Other topical medications for psoriasis include Zithranol-RR (Anthralin), vitamin D3 or A, coal tar and salicylic acid. Anthralin has no long-term side effects, though it may cause skin irritation and may stain light-colored hair and unaffected skin. 14

For moderate or severe psoriasis, affecting more than 3% of the body surface area, topical treatments are generally not effective and more aggressive therapy is required. Phototherapy is an effective second line treatment for moderate psoriasis or mild disease that has not responded to topical therapy. Phototherapy consists of regularly exposing the skin to ultraviolet (UV) light which reduces inflammation by reducing T-cell proliferation. Ultraviolet light treatment is classified as UVA and UVB. UVA light is the principle component of sunlight and it is used in combination with photosensitizing medications such as psoralen when it is referred to as PUVA. The disadvantages of UVA and PUVA treatments include a high risk of cancer along with immediate reactions including, nausea, headache, burning of the skin and photosensitivity. Use of topical PUVA or baths have been proven to be a safer and effective alternative. 22-23

UVB treatment is based on another component of sunlight and it is available as broadband or narrowband therapy. Broad band UVB phototherapy uses light with a wavelength range between 290 and 350 nanometers. UVB treatment is less carcinogenic when compared to UVA and does not require co administration of medications. However, it may be less

effective. Narrowband UVB uses light in the 311-313 nanometer wavelength range. It is highly effective and does not require the use of photosensitizing medications. 22-23

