#### general aim.

With respect to Psoriasis, adalimumab has been approved in Canada for patients with moderate to severe Psoriasis that are candidates for systemic therapy. For patients with moderate plaque Psoriasis adalimumab should be used for after phototherapy has been ineffective or inappropriate (Canadian Product Monograph). To date real — life observational data allowing the comparison of the effectiveness of adalimumab to topical agents and traditional systemic agents in patients failing current treatment have not been reported. There is also currently a knowledge gap with respect to the practice patterns and regional variation in the approach used by Canadian physicians in the management of patients with psoriasis.

Psoriasis presents a significant burden of illness through the physical and emotional manifestations that significantly affect the patient's quality of life as well as loss of productivity and direct and indirect costs. Assessment of the impact of different approaches to the management of moderate to severe psoriasis on these patient centric outcomes is therefore of paramount importance. Given that patient reported outcomes have a cultural and regional influence, the assessment of these outcomes in specific regions is also of high relevance and importance in the assessments of regional and global benefit – risk ratios.

An important consideration of Psoriasis is the fact that approximately 30% of the patients develop psoriatic arthritis (PsA). To date, there are no known predictors of progression to PsA among patients with psoriasis. In addition, it is known that triggers of psoriasis flare ups and disease progression have an environmental and genetic determinant. There is currently a knowledge and patient management gap with respect to the screening and detection of flare – up triggers or articular and extra articular signs and manifestations indicating progression of psoriasis or onset of PsA. There is therefore a general need for the assessment of these questions. However, given the potential genetic and environmental effect on the incidence of Psoriasis as well as it severity and progression,

these questions must be addressed at the regional level.

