# 6.0 Investigational Plan

This is a Canadian Post Marketing Observational Study utilizing a prospective cohort design. Patients are entered into the study cohort at the time of change of their Psoriasis treatment for any reason and are followed for a maximum of 24 months with recommended assessments at 3, 6, 12, 18 and 24 months after baseline. Treatment of the patients and follow up will be according to the physician's judgment, regional regulations and the product monograph. Off-label use will not be permitted and these patients will not be included in the study. Dose changes including escalation will be allowed as per the physician's judgment for patients that were treated as per indication when they were enrolled in the study.

There will be 660 patients enrolled from the practices of approximately 30 - 40 dermatologists across Canada. The study sample will be randomly selected and proportional to the Canadian population and distribution of dermatologists in Canada.

The following patient cohorts will be defined:

i. Initiated treatment with a new topical agent that was not used before or already on treatment with a topical agent and not responding requiring a change of treatment

type, frequency or dose.

- ii. Initiated treatment with a new systemic agent that was not used before alone or in combination with topical agents.
- iii. Initiated on treatment with adalimumab alone or in combination with topical agents.

In the case that the patient is switched from one cohort to another during the course of the study, follow up will continue as per the study protocol. For these cases, the treatment will be considered as a time dependent variable in the assessment of the study outcomes. In addition, depending on the number of patients switching cohorts, separate cohorts may be defined to include those patients that change treatment during the study.

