#### 10.3 Sample Size Calculations

Sample size considerations are based on the primary objectives of the study, specifically the proportion of patients that achieve a PGA rating of "0" or "1" at 24 months of follow up.

The following data and assumptions were used to determine the sample size requirements for the study:

- In the Champion study after 16 weeks of treatment 73% of the patients treated with adalimumab, 30% of the patients treated with methotrexate and 11.3% of the patients treated with placebo achieved PGA values of 0 or 1 indicating clear or minimal disease.
- The Champion study was a randomized placebo controlled clinical trial that was based on a strict protocol not allowing any concomitant treatment and enrolling a very well defined patient population. In the current study we can assume that we will observe similar trends in the order of treatment effectiveness, by which adalimumab will be superior to traditional systemic agents, which will be superior to topical agents. However, due to case mix and use of concomitant medications the actual therapeutic effect and difference between groups may be more variable and lower than that observed in the CHAMPION study. We can therefore assume that due to patient profile, and in order to be conservative, that the observed proportion of patient achieving and maintaining a PGA≤ 1 at 6 months will be approximately 50%. A relative reduction of 20% (RR = 0.80) in PGA would be considered as the minimum acceptable for clinical importance. Therefore, the current study we should be powered to detect a 20% relative reduction between adalimumab and traditional systemic agents, and a similar difference between systemic and topical agents. It follows that if we assume that the proportion of patients treated with adalimumab that achieve PGA ≤1.0 at six months will be

50%, the proportion in the patients treated with traditional systemic agents will be 40% ( $\underline{RR}$ =0.8) and that in patients treated with topical agents will be 32% ( $\underline{RR}$  = 0.8).

• For an expected treatment group ratio of 1:1 for adalimumab: traditional systemic agents and topical agents a total of 360 (180: 180) patients will be required for 80% power and two tailed significance of 5%. Assuming a 25% attrition rate and allowing for 100 additional patients (10 per variable) in the multivariate analysis 660 (330:165:165) patients will be recruited.

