## 3 Statistical Methods

## 3.1 Statistical Handling Policy

### 3.1.1 Analysis Conventions

This section details general guidelines to be used for the statistical analyses. Deviations from these general policies may be given in the specific detailed sections of this statistical analysis plan. When this situation occurs, the rules set forth in the specific section take precedence over the general conventions. The following policies will be applied to all data presentations and analyses:

- Two-tailed tests will be performed for all analyses that use statistical testing with a significance level of  $\alpha = 0.05$ .
- All p-values will be rounded to 3 decimal places. All p-values that round to 0.000 will be presented as '<0.001' and p-values that round to 1.000 will be presented as '>0.999'. Any p-value  $\leq$ 0.05 will be considered statistically significant.
- Summary statistics will consist of the number and percentage of responses in each category for discrete variables, and the mean, median, standard deviation (SD), minimum, maximum, and 95% confidence interval for continuous variables.

COMPLETE - PS Statistical Analysis Plan Version 3.0 July 23rd, 2015 Page 24 of 231

- All mean and median values will be formatted to one decimal place. Standard deviation values will be formatted to two decimal places.
- All percentages will be rounded to one decimal place. Where appropriate, the number and percentage of responses will be presented in the form XX (XX.X %), where the percentage is in the parentheses.
- All listings will be sorted for presentation in order of treatment group, site number, subject number, and date of procedure or event.
- When necessary for analysis purposes, partial dates will be completed (i.e., turned into complete dates) using the most conservative approach. Where appropriate, all analysis and summary tables will have the population sample size for each treatment group in the column heading.
- All analyses and summary tables will have the population sample size for each treatment group in the column heading.
- Tables will include footnotes describing the analyses involved, and listings of covariates included in the analyses, where relevant.

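### SAP 3.10 does not guarantee adjustment for baseline phototherapy and has no analysis of phototherapy received before the month-6 PGA

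*SAP*

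**What the plan says.** The primary outcome is the proportion with PGA of 1 or less at 6 months (protocol 5.3.1, SAP 2.10.1.1). SAP 3.10 says between-group differences in it "will be assessed with simple logistic regression analysis and multivariate logistic regression models adjusting for potential confounders or the propensity score". SAP 3.8 fixes what counts as a potential confounder: a baseline variable that differs between cohorts at P<0.15 or by more than two-fold. SAP 3.2 adds that the choice among covariates, propensity scores and stratification will be driven by the data.

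The cohorts are defined by the drug started or changed. The first begins "Initiated treatment with a new topical agent that was not used before or already on treatment with a topical agent". The systemic and adalimumab cohorts mention only topical agents as combination treatment (protocol 6.0, SAP 2.4). Neither the cohort definitions nor the exclusion criteria mention phototherapy.

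Elsewhere the documents treat it as an active therapy. Protocol 3.0 states: "Phototherapy is an effective second line treatment for moderate psoriasis or mild disease that has not responded to topical therapy". Protocol 4.0 says that in moderate plaque disease "adalimumab should be used for after phototherapy has been ineffective or inappropriate". Use of phototherapy is collected at baseline and at every follow-up visit (Table 1), and change in its use is secondary endpoint xiii. For follow-up, SAP 3.9 lists "changes in psoriasis medications/treatments, including phototherapy" among the items to be summarised descriptively.

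**The concern.** Phototherapy can change the month-6 PGA, and the documents connect it with which treatment a patient is given. A baseline variable with both properties is a confounder on subject-matter grounds. Whether it is adjusted for should not depend on a significance test of cohort differences, because an imbalance that misses P<0.15 can still bias the estimate.

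Phototherapy started or continued after baseline is a separate gap. A patient who reaches PGA 0 or 1 with its help counts as a responder to the cohort agent, and nothing in 3.10 shows how far the result depends on such patients. If use differs between cohorts, the contrast is partly a contrast in phototherapy use. Because 3.2 leaves the adjustment approach open, any remedy chosen after the data are seen would be hard to defend.

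**Working it through.** **1. Do the existing rules reach phototherapy at month 6?**

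- *SAP 3.8 screen.* It works on baseline characteristics. Baseline phototherapy can enter through it but need not. Use begun after baseline cannot.
- *Switching rule (protocol 6.0, SAP 2.4).* Treatment becomes time dependent when a patient moves from one cohort to another. Adding phototherapy is not such a move.
- *Regimen-change rule (protocol 10.2, SAP 3.11).* This wording is broader and refers to changes in regimen. The SAP places it under the secondary objectives, and a logistic model of one outcome at one time point does not use a time-dependent covariate.
- *SAP 3.10.* It has no term, response rule or supplementary analysis for phototherapy.

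**2. Inputs for an illustration**

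- Planned response rates: adalimumab 50%, systemic 40%, topical 32% (protocol 10.3).
- Recruitment 330:165:165 with 25% attrition (protocol 10.3): 330 × 0.75 = 247.5 and 165 × 0.75 = 123.75, taken as 247 and 124.
- Significance level (SAP 3.1.1): "Two-tailed tests will be performed for all analyses that use statistical testing with a significance level of" 0.05.
- Assumed, because the documents give neither: the share *s* of a cohort given phototherapy by month 6, and the response rate *r* among those patients.

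**3. The plan's own figure**

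Protocol 10.3 states 360 patients (180:180) for 80% power. The two-proportion formula with pooled variance gives 388 per group for 50% v 40%, and 196 per group (392 in total) for 50% v 36%, the mean of 40% and 32%. So 360 is not reproduced. That is a separate matter; this point uses only the planned rates and the recruitment numbers.

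**4. Formulas**

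- Diluted rate = (1 − *s*) × planned rate + *s* × *r*.
- Power = Φ[(d − 1.96 × SE0) / SE1], where d is the difference, SE0 uses the pooled proportion and SE1 the separate proportions.

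With no phototherapy, 50% v 32%: the pooled proportion is (247 × 0.50 + 124 × 0.32)/371 = 0.440, SE0 = 0.0546, SE1 = 0.0526, and (0.18 − 1.96 × 0.0546)/0.0526 ≈ 1.39. Power is 91.7%.

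**5. Phototherapy in the topical cohort only**

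| *s* | *r* | Topical rate | Difference (points) | Power at 247:124 |
|---|---|---|---|---|
| 0 | – | 32.0% | 18.0 | 91.7% |
| 10% | 50% | 0.9 × 32 + 0.1 × 50 = 33.8% | 16.2 | 84.9% |
| 20% | 60% | 0.8 × 32 + 0.2 × 60 = 37.6% | 12.4 | 62.0% |

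**6. Other patterns of use, at *s* = 20% and *r* = 60%**

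- Equal use in all cohorts: adalimumab 0.8 × 50 + 12 = 52%, systemic 0.8 × 40 + 12 = 44%, topical 37.6%. The differences become 8 points (planned 10) and 14.4 points (planned 18).
- Use in the adalimumab cohort only: 52% v 32%, a difference of 20 points. The contrast grows.

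**7. What a non-responder rule would do**

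With *s* = 20% in the topical cohort only, counting those patients as non-responders gives 0.8 × 32 = 25.6%, a difference of 50 − 25.6 = 24.4 points. The as-used difference is 12.4, and without phototherapy it is 18. The rule overshoots, so it can only be supportive.

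**The case against.** The objective is real-life effectiveness under treatment by physician judgment, so an estimate that includes phototherapy as it was used is a legitimate target. That stands, and the fix keeps it as the main result.

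A reader might infer more than the documents support, in four ways:

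- *That the design makes phototherapy use uneven and so biases the result against adalimumab.* The label wording makes uneven use plausible but does not rule out concurrent use. Both documents also place systemic agents after topical agents or phototherapy have failed, so systemic patients sit at a similar point in the sequence. No use rates are given.
- *That the sizing assumes comparators free of co-treatment.* Protocol 10.3 describes the source trial as run under a "strict protocol not allowing any concomitant treatment", but it does so to explain why smaller effects are planned here. The rates move from 73%, 30% and 11.3% to 50%, 40% and 32%, partly for concomitant medication. Some dilution may therefore already be in the 32%, and the table above may count it twice.
- *That regimen changes are handled only when a patient moves cohort.* Protocol 10.2 and SAP 3.11 are broader than that. The supportable statement is that this rule does not reach the month-6 logistic model.
- *That phototherapy use goes unreported, or that a change to phototherapy alone could fall into a cohort.* Its use is a secondary endpoint and is described at follow-up, and every cohort already requires a topical, systemic or adalimumab start or change.

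The mock tables are not in the text available, only their list. Whether the covariate footnotes mention phototherapy cannot be checked.

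**Conclusion.** The point holds as two specific gaps in SAP 3.10. Adjustment for baseline phototherapy is left to a P-value or two-fold screen, and no analysis addresses phototherapy received between baseline and the month-6 PGA. If concurrent use differs between cohorts, the primary contrast mixes the effect of phototherapy with that of the cohort agent.

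Direction and size cannot be determined from the documents. The fall in power from 92% to 85% or 62% assumes use in the topical cohort only, invented use and response rates, and an unadjusted comparison. It shows that moderate use could matter, not that it will. The as-used estimate is not wrong for this objective. This is an inexpensive improvement to the analysis plan, not a flaw that invalidates the study.

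**What to change.** Amend SAP 3.10 as follows:

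1. Include baseline phototherapy use, and prior phototherapy where recorded, in both the adjusted logistic model and the propensity score, whatever the result of the 3.8 screen.
2. Keep the as-used month-6 estimate as the main result and say in its label that it includes phototherapy as used.
3. Pre-specify one supplementary month-6 analysis, applied identically in all three cohorts, in which a patient who received phototherapy between baseline and the month-6 PGA is not counted as a responder to the cohort agent. Show phototherapy use by cohort beside it.

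The data are already collected at each visit and patient care does not change. The cost is SAP wording, one or two extra covariates and a second estimate to explain. That estimate conditions on care chosen after baseline and may favour the cohort with less phototherapy, so the SAP should state that it is supportive only.
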